#### Randomization

A computerized randomization scheme will be developed to randomize which teeth will be in the study and which group each tooth will be in. The "sample function" in R version 3.1.2 will be used. Assignment of study teeth and treatment allocation will be recorded in each subject's Case Report Form (CRF).

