#### Blinding

The restoration grading investigator and the subject will be blinded as to which group each restoration is in.

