#### Visit 1 (Approximately 1 hour): Screening

The subjects will be instructed to read the informed consent form (ICF). Subjects will be given ample time to have any questions answered. If a subject decides to participate, he or she will be instructed to sign the ICF. A copy of the ICF will be given to the subject.

Subject will be asked to complete demographic information and a medical history.

An oral exam, including evaluation of oral cavity, soft and hard tissues, will be completed following standard of care procedures in US dentistry using a mouth mirror and dental explorer.

Radiographs (bitewings) will be taken if none exist that are less than 1 year old and of diagnostic quality. It is within standard of care to take radiographs for caries detection if none less than 1 year old exist.

Inclusion/exclusion criteria will be evaluated.

If you are eligible to continue in the study, randomization will occur.

Periapical radiographs will be taken on the randomized teeth (if none exist that are less than 1 year old and of diagnostic quality). It is standard of care to have periapical radiographs prior to class II restorations to ensure there are no signs of periapical pathology.

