# *Visit 2 (May occur same day as Visit 1 and up to 1 month after Visit 1)(1.5-2 hours):Restoration Placement*

Medical history will be reviewed and any changes will be noted.

Eligibility and subject withdrawal criteria will be reviewed to ensure the subject still qualifies for the study.

Oral exam will occur as at Visit 1.

Intraoral photographs will be taken (photographs will only be intraoral, no facial photographs will be taken).

Sensitivity will be assessed on randomized teeth. Subjects will be asked if they experience any sensitivity on the randomized teeth. If yes, they will be asked to rate their sensitivity on a scale of 1-100.

Group 1: SonicFill™ 2 Restoration

Local anesthesia will be achieved following standard of care.

Composite shade will be chosen.

Rubber dam or other appropriate isolation will be placed following standard of care.

Tooth will be prepared for restoration following standard of care (using handpieces, burs, hand instruments, etc. as needed). All decay will be removed.

Etching and bonding will be achieved using Optibond XRT following manufacturer's instructions.

Restoration will be placed and cured using SonicFill 2 following manufacturer's instructions.

Finishing and polishing steps will be completed using Axis ProGloss Polishing System.

Group 2: Filtek™ Supreme Ultra:

Local anesthesia will be achieved following standard of care.

Composite shade will be chosen.

Rubber dam or other appropriate isolation will be placed following standard of care.

Tooth will be prepared for restoration following standard of care (using handpieces, burs, hand instruments, etc. as needed). All decay will be removed.

Etching and bonding will be achieved using Scotchbond Universal following manufacturer's instructions.

Restoration will be placed and cured using Filtek™ Supreme Ultra following manufacturer's instructions.

Finishing and polishing steps will be completed using Axis ProGloss Polishing System.

Intraoral photographs will be taken.

Restorations will be evaluated by the grading investigator (an investigator other than who placed the restorations) according to Hickel criteria (Appendix A).

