#### Radiographs

All radiographs will be taken digitally following standard of care procedures, including the subject wearing a lead apron. The radiographs used in this study contain no more radiation than would be used in a customary dental procedure. It is within standard of care to take radiographs for caries screening if radiographs that are of diagnostic quality from within the past 1 year do not exist. It is within standard of care to take radiographs yearly for evaluation after restoration placement. Radiographs will be taken at the one-year and two year recalls. In the event an adverse event is suspected, it is clinically necessary, or due to a dental emergency a radiograph may be taken at the time of the AE or emergency, but it is not the norm for this trial.

At radiograph time, all female subjects will be questioned regarding pregnancy. Any responding positively at the time of screening will be excluded in accordance with the inclusion/exclusion criteria. If a subject becomes pregnant during the course of the study, radiographs will be delayed until after delivery. Subjects unwilling or unable to have dental radiographs will be excluded from the study.

Appointment	Visit 1 Screening	Visit 2 Baseline	Visit 3 6 month	Visit 4 1 year	Visit 5 2 year
Procedures					
Informed Consent Form	Х				
Demographics	Х				
Medical History	Х	Х	Х	Х	Х
Evaluate eligibility and withdrawal criteria	х	x	х	Х	х
Oral Mucosal Tissue Examination	x	x	х	Х	Х
Radiographs	If needed			Х	Х
Randomization	Х				
Intraoral Photographs		Х	Х	Х	Х
Sensitivity Assessment		Х			
Restoration Placement		Х			
Hickel Criteria Grading		Х	Х	Х	Х
Adverse Event Assessment		X	X	Х	Х
Stipend	X	X	X	Х	Х

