If after going through the consent form, the participant indicates s/he would like to discuss the study with associates or think about participating, then the meeting will be ended and the participant will be asked to contact the study when s/he makes her decision. If the participant contacts the study in the future for participation, s/he will be invited back to the clinic, and if informed consent is given at that time, study activities will begin then.

If the participant indicates s/he may be interested in participating after going through the consent form with the investigator, and the investigator determines the participant has the capacity to provide informed consent, the participant will be asked to provide informed consent at that time. Patients will certify their willingness to participate in the study by signing and dating the IRB approved informed consent document. The subject will be given a copy of the consent form.

If any new finding requires any change to the informed consent form, the subject will be re-consented.

Non-English speaking subjects will not be enrolled in the study because study staff at this time are not certified, prepared, or trained to translate or communicate in any language other than English. The study budget does not allow for the payment of translation services at this time. There are no direct benefits to this population by participating in this study.

3) Study Location

Tufts University School of Dental Medicine

Clinical Evaluation of Kerr SonicFillTM 2 vs 3M ESPE FiltekTM Supreme Ultra Universal Restorative PI: [name], DMD, MS, PhD

4) Personnel

Ongoing communication with the IRB and sponsor – The PI Obtaining consent – The PI or his representative Conducting screenings – The PI or Co-Is Placement of restorations – The PI or Co-Is Evaluation of restorations – The PI or Co-Is (who did not place restoration) Maintaining paperwork – The PI and/or study coordinator

- 5) Anticipated Study Timeline\*
  - Protocol and ICF Submission to the IRB: September 2016
  - Approval by the IRB: October 2016
  - Subject Recruitment, Screening, Enrollment and Randomization: June 2017-December 2017
  - Placement of Restorations- June 2017-January 2018
  - Initial Report- January 2018-February 2018
  - Six Months Follow up- December 2017- June 2018
  - Six Months Report- July 2018-August 2018
  - One year follow up- June 2018-December 2018
  - One year Report- January 2019- February 2019

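### Does writing the treatment allocation in each subject's CRF undo the blinding of the grader?

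*Combined protocol and SAP*

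**What the plan says.** The Randomization section has a computer-generated scheme choose the study teeth and their groups, then states: "Assignment of study teeth and treatment allocation will be recorded in each subject's Case Report Form (CRF". The Blinding section adds: "The restoration grading investigator and the subject will be blinded as to which group each restoration is in".

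Under Visit 1 the timing is: "If you are eligible to continue in the study, randomization will occur". Section I.4 (Personnel) gives the roles:
- "Conducting screenings – The PI or Co-Is"
- "Evaluation of restorations – The PI or Co-Is (who did not place restoration"
- "Maintaining paperwork – The PI and/or study coordinator"

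The visit procedures repeat the separation at Visits 2 to 5: "Restorations will be evaluated by the grading investigator (an investigator other than who placed the restorations". The Subject Timeline table places "Adverse Event Assessment" on those same visits, and the Adverse Events section has events entered on CRFs. The CRF itself is not among the documents.

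**The concern.** The trial is described as examiner-blinded, yet the allocation sits in a document that the study team opens routinely. Not having placed a restoration removes one source of knowledge and leaves the written record untouched. The PI and Co-Is form one pool for screening, placement and grading, and the PI may also keep the paperwork. The rules on confidentiality and data access make no exception for the grader.

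The stakes would be real. The five esthetic criteria are judged by eye on verbal scales. The main outputs are within-subject percentages: how often one material outperforms the other, and how often they are equal. A grader who knew which tooth had which material could shift a one-step difference in either direction, or towards equality, which is what the hypothesis expects. The confidence intervals would not reveal it.

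**Working it through.** No figure in the plan bears directly on this point, so the check is mainly a comparison of the sections, with a little arithmetic for scale.

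**1. Do the two rules conflict?** The Randomization section says where the allocation is documented. The Blinding section says who may not know it. Both hold if the grading page does not show the allocation. A conflict would need a statement that the grader works from the page carrying the allocation, and there is none.

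**2. Does any grader task need the allocation?**
- Visit 1: eligibility is assessed before randomization. The periapical radiographs that follow need to know which teeth are in the study, not which material each will receive.
- Visit 2: the sensitivity question before treatment also needs only the tooth numbers. The operator needs the allocation, and the operator is barred from grading.
- Visits 2 to 5: the Appendix A scales describe the state of the restoration and tooth, so a grade can be entered by tooth number. The analyst can join grades to allocation afterwards.

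**3. Does the overlap of roles force exposure?** The title page lists several Co-Investigators, so a grader with no other role for a given subject is available. Paperwork is given to the PI and/or the coordinator, so Co-Is are not named for it. The overlap therefore arises only where the PI both keeps the paperwork and grades the same subject, which no section requires. The plan does not say that the grader carries out the adverse event assessment.

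**4. Counts of opportunity.**
- Hickel grading: Visits 2, 3, 4, 5. Adverse event assessment: Visits 2, 3, 4, 5. Overlap: 4 of 4.
- Categories: 5 esthetic + 5 functional + 4 biological = 14. Esthetic share: 5/14 = 36%.

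Neither count measures how often a grader sees an allocation, or what follows if one does.

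**5. Scale, if grades were altered.** The plan's stated margin of error reproduces: 1.96 × √(0.25/35) = 0.1656, or 16.6%. With 35 pairs, each altered comparison moves a percentage by 1/35 = 2.9 points. Shifting a percentage by the full margin would take 0.1656 × 35 = 5.8, so about six pairs altered in the same direction. This is arithmetic on a hypothetical, not an estimate of bias.

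**6. Timing.** The version date is 11/2/2018. The anticipated timeline ends randomization in December 2017, placement in January 2018 and six-month follow-up in June 2018. One-year follow-up runs June to December 2018 and two-year follow-up June to December 2019. If that held, new rules for releasing the allocation at Visits 1 and 2 could no longer be applied, and only the remaining one-year and the two-year gradings could benefit. The timeline is marked as subject to change.

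**The case for a change.** The strongest case for a change is that a blinding requirement without a procedure relies on each grader not looking. The access rules admit study personnel in general, no one is named as holder of the allocation, and no allocation-free grading form is described. The remedy would be cheap (a separate form kept by the coordinator), and the two-year grading was probably still to come.

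Part of this stands. The plan gives no record-handling procedure, and the documents cannot show that the CRF pages are separate. But the access rules sit under Confidentiality and serve to keep outsiders out. They do not override the specific rule for the grader. Nor would a lapse go unaddressed: a grader who consulted the allocation would depart from the Blinding section, and section L (Protocol Deviations) requires deviations to be reported to the IRB and included in the final report.

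A sealed allocation record would also raise a question the plan does not answer. The CRF entry for an unanticipated device effect covers relatedness to the test device, and the PI, who may grade, deals with the sponsor and IRB. Closing the record to graders would require deciding who makes that assessment.

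**Conclusion.** No change to the plan follows. The plan requires blinded grading and separates grader from operator, and nothing in it obliges a grader to see the allocation. If the grading page did show the allocation, the site would be breaching the Blinding section; that would be a fault of conduct, not of the plan. Keeping grades and allocation on separate pages is the ordinary way to meet both rules, and it can be done in the CRF layout without new protocol text.

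The documents show neither unblinding nor bias, and the size of any bias cannot be derived from them. The conclusion assumes that the site applies the blinding rule as written and that the CRF, which cannot be seen here, allows it. Sample size, margin of error and analysis are unaffected either way.

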#### Blinding

The restoration grading investigator and the subject will be blinded as to which group each restoration is in.

#### C) Products

All study materials – SonicFill™ 2, SonicFill™ 2 Handpiece and coupler, Optibond XRT, Scotchbond™ Universal and Filtek™ Supreme Ultra resin composite will be provided by Kavo Kerr Group and have received 510(k) clearance from the United States Food and Drug Administration (FDA) as Class II non-significant risk medical devices. All products will be used according to their FDA clearance in this study.

Group	Resin Composite	Bonding Agent
1	SonicFill™ 2	Optibond XRT
2	Filtek ™ Supreme Ultra	Scotchbond ™ Universal Adhesive

Receipt and usage of the clinical study supplies and products will be documented in the study file. The study materials will be stored in a locked closet/cabinet and will be accessible only to the research team members. Products may be stored at room temperature. The sponsor may request that some supplies be returned at the end of the study.

#### Restriction in Device Use

The Principal Investigator is responsible for limiting access of the device to participants in this trial and ensuring it is used only as specified in the protocol. The device shall be stored as specified by the sponsor.

#### SonicFill™ 2

SonicFill™ 2 is, a sonic-activated, bulk fill dental composite system for posterior restorations that requires no additional capping layer. Proprietary sonic activation enables a rapid flow of composite into the cavity for placement and adaptation.

#### OptiBond XTR^12

OptiBond XTR self-etch, light-cure universal dental adhesive Universal compatibility enables use for all direct and indirect restorations. The self-etch primer and adhesive in this 2-bottle system brings increased bond strengths to uncut enamel and dentin. OptiBond XTR uses GPDM (glycerophosphoric acid dimethacrylate, an phosphate based adhesive monomer) technology, ternary solvent system, filled adhesive and optimized formulation to produce adhesion for direct and indirect procedures.

Filtek™ Supreme Ultra Universal Restorative Filtek™ Supreme Ultra is a Universal Nanocomposite dental restorative material that is visible-light

activated, designed for use in anterior and posterior restorations of any class. This restorative material is available in a wide variety of Dentin, Enamel, Body, Translucent shades, and all shades are radiopaque. Filtek™ Supreme Ultra uses nanofiller technology to give restorations polish retention.

#### Scotchbond™ Universal Adhesive

Scotchbond™ Universal is a single-bottle adhesive solution for all surfaces, and can be used in total-etch, self-etch or selective-etch mode for both direct and indirect restorations. Scotchbond™ Universal provides consistent bond strength to both moist and dry etched dentin, without additional primer.

- D) Subject Characteristics
  - 1) Inclusion Criteria

To be considered eligible for this study, each patient must meet all criteria listed below:

- Is at least 18 years of age
- Is willing to provide voluntary written informed consent
- Is in good medical health and able to tolerate the dental procedures
- Has 1 pair of qualifying molars or premolars that require Class II restorations. Patients with more than 2 cavities may be enrolled but the additional teeth will not be included in the study.
- Restorations must have a buccal to lingual/palatal width equal to or greater than 1/3 the distance from buccal to lingual/palatal cusp tips
- Study teeth must be in occlusal function and must also be in contact with the neighboring tooth on at least one surface
- Study teeth must be vital (i.e., free of clinical signs and symptoms of periapical pathology)

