#### III) Research Plan

A) Experimental Design

This study is a randomized, split-mouth, controlled, examiner-blinded clinical evaluation of Class II restorations using a new bulk-fill composite (SonicFill™ 2) and comparing it to 3M ESPE Filtek™ Supreme Ultra resin composite placed in the traditional incremental technique.

B) Sample Size and Statistical Analysis

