#### Statistical analysis

Tables of descriptive statistics (counts and percentages for categorical variables, means and standard deviations for continuous variables) will be prepared to summarize the demographic characteristics of the patients, the distribution of restorations and baseline data, and to illustrate the recall and data analysis findings. Because the hypothesis of the study does not involve superiority of one technique over another, and comparable results between SonicFill™ 2 and Filtek™ Supreme Ultra are anticipated, confidence intervals will be used rather than p-values. In particular, for each evaluation category, the percentage of times that SonicFill™ 2 outperforms Filtek™ Supreme Ultra, the percentage of times that Filtek™ Supreme Ultra outperform SonicFill™ 2, and the percentage of times with equal performance will be calculated along with 95% confidence intervals. Frequency distributions will also be calculated for each combination of technique and evaluation category, along with 95% confidence intervals. SPSS (Version 22) and R (Version 3.1.2) will be used in the analysis.

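### No rule stops the two study restorations from facing each other across one interproximal space, where mucosa, contact and partly caries grades cannot be credited to one material

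*Combined protocol and SAP*

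**What the plan says.** Section III.A describes the trial as a "randomized, split-mouth, controlled, examiner-blinded clinical evaluation of Class II restorations". It does not define split-mouth by side, quadrant or arch.

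The inclusion criteria (III.D.1) ask for a patient who "Has 1 pair of qualifying molars or premolars that require Class II restorations". They add: "Study teeth must be in occlusal function and must also be in contact with the neighboring tooth on at least one surface". Patients with more than two cavities may enter, with the extra teeth left out of the study. The exclusion criteria (III.D.2) contain nothing on tooth position.

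The Randomization paragraph (III.B) says that a computerized scheme will "randomize which teeth will be in the study and which group each tooth will be in", using the sample function in R. It mentions no positional constraint. It does say that the study teeth and their allocation are recorded in the Case Report Form (CRF).

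The objectives (I.A) list 14 categories, among them approximal contact point, adjacent mucosa and recurrence of caries. The Statistical analysis paragraph (III.B) counts, for each category, how often each material does better, and "the percentage of times with equal performance will be calculated along with 95% confidence intervals".

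**The concern.** The comparison is made entirely within the mouth, so it works only if each tooth's grade reflects its own material. Two Class II restorations that face each other share one papilla and one contact. A faulty contour on either can affect the mucosa and contact graded for both, and a new carious lesion in that space may be hard to assign to one of them. The required neighboring contact may itself be with the other study tooth. When more than two teeth qualify, the random draw can select two neighbors although a separated pair was available.

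The direction matters because of how the hypothesis is framed. The analysis paragraph gives as its reason for preferring intervals to p-values: "Because the hypothesis of the study does not involve superiority of one technique over another". Comparable results are anticipated, and no margin is set. Where both teeth are graded on one site, matching grades are likely. A tie produced by the shared site would then be read as evidence of comparability.

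**Working it through.** **The plan's own figures.** The worst-case half-width of a 95% interval with 35 pairs is 1.96 × √(0.25/35) = 0.1657, or 16.6 points, as stated. Allowing for 20% dropout, 35/0.80 = 43.75, rounded up to 44, also as stated. Neither figure depends on tooth position.

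**Which categories are exposed.** Of the 14 categories, adjacent mucosa and approximal contact describe the shared space, and recurrent caries does so in part. Luster, surface and marginal staining, color match, esthetic form, material fracture, marginal adaptation and tooth integrity are graded on the individual tooth or restoration.

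**How common such pairs might be.** The documents do not say. As a rough guide, assume that two study teeth are drawn uniformly from all posterior teeth:

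- Four posterior teeth per quadrant: 3 neighboring pairs × 4 quadrants = 12 of 16 × 15/2 = 120 pairs, or 10.0%.
- Five per quadrant (third molars included): 4 × 4 = 16 of 20 × 19/2 = 190 pairs, or 8.4%.

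Only neighbors whose restored surfaces face each other share a space, so under this assumption the share is below these figures. Real cavities need not be spread uniformly, so the true share could be lower or higher.

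**Dilution in an exposed category.** Let f be the share of pairs with a shared space and c the share of those that become ties. A true percentage p favoring one material is then observed as p × (1 − f × c). With p = 20% and f = 10% (both assumed):

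| c | Observed percentage |
|---|---|
| 0.5 | 0.20 × (1 − 0.05) = 19% |
| 1 (upper bound) | 0.20 × (1 − 0.10) = 18% |

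Ten percent of 35 is 3.5 pairs. If the truth were 60% equal, 30% favoring one material and 10% favoring the other (assumed), then f = 10% and c = 1 give 0.60 + 0.10 × 0.40 = 64% equal. The net difference falls from 20 to 20 × 0.90 = 18 points.

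**Against sampling error.** At a true 20%, the half-width with 35 pairs is 1.96 × √(0.16/35) = 0.133, or 13.3 points. A 2-point shift is small beside that. It is systematic, however, and the interval does not reflect it.

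**The case against.** The strongest reply is that the effect is narrow and its direction is inferred. Most of this stands.

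- **A reader might infer that the whole paired comparison is pushed toward equality.** The documents do not support that. Most of the 14 categories have no shared site.
- **A reader might also count opposing teeth as forced ties.** They share no papilla and no interproximal contact. Wear or loading between them could create a difference as easily as hide one. Under the same uniform draw, with four posterior teeth per quadrant, adjacent plus opposing pairs reach at most (12 + 14)/120 = 21.7%. Forcing ties in 22% of pairs would raise a true 60% equal to 0.60 + 0.22 × 0.40 = 68.8%. If instead one restoration's defect lowered only the other tooth's grade in a quarter of such pairs that were truly equal, the figure would fall to 0.60 − 0.22 × 0.25 × 0.60 = 56.7%. The sign is not known.
- **Contact scoring cannot be checked.** In the copy available, Appendix A shows no column for approximal contact, which may be a fault of the copy. Whether one fault downgrades both teeth is therefore unclear.
- **Split-mouth may have been meant as opposite sides, and the R scheme, still to be developed, may have contained a constraint.** Either is possible, but the plan states neither.
- **Much of the design fix may come too late.** This version is dated 11/2/2018. The anticipated timeline, which is subject to change, puts placement in June 2017 to January 2018.

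The gap in the pairing rules survives all of these replies. So does the attribution problem for the few shared-site categories.

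**Conclusion.** The point holds in a limited form. The plan as written permits study restorations that share an interproximal space. For those pairs, the comparisons of adjacent mucosa and approximal contact, and partly recurrent caries, do not isolate the material. A drift toward ties is the probable direction in these categories, but that is a judgment from how they are graded; the documents do not state it.

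The size cannot be fixed without the tooth positions. The fall from 20% to 18% rests on an assumed 10% share with every such pair tied, so it is the largest dilution that this share could produce. Larger shares can be imagined, but the documents give no basis for them. A reader might also infer that the sample size is wrong; on this point it is not, and 35, 44 and 16.6% all stand. The change is worth making because it is cheap and replaces an unknown with a reported count.

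**What to change.** 1. **Randomization (III.B).** When more than two teeth qualify, restrict the random draw to pairs that do not share an interproximal space, and randomize material within the chosen pair as now. This is one constraint in the R code and costs no recruitment where such a pair exists.
2. **Inclusion criteria (III.D.1).** State the same requirement for any subject still to be enrolled, and say what split-mouth means. The cost is some extra screen failures among patients whose only two qualifying cavities face each other. On the anticipated timeline, this may apply to few or no subjects.
3. **Pairs already treated.** From the tooth assignments in the CRF, together with the surfaces restored, report how many pairs share a space. Repeat the adjacent mucosa, contact and caries comparisons without them as a sensitivity analysis, keeping the full set as the main result. The cost is precision: with 31 or 32 pairs the worst-case half-width is 0.98/√31 = 17.6 or 0.98/√32 = 17.3 points, and with 28 pairs it is 0.98/√28 = 18.5 points, against 16.6 with 35.
4. **Opposing pairs.** Report their number and results separately, without assuming a direction.
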